5.2.4 Oxaliplatin

5.2.4.1 Calculation of oxaliplatin dose

Doses for oxaliplatin will be administered on the basis of milligrams of drug per square meter of body surface area (BSA) as measured at baseline (mg/m^2) , up to a maximum value of 2 m², and should be rounded to the nearest 10 mg.

5.2.4.2 Administration of oxaliplatin

Oxaliplatin will be administered as a 2-hour intravenous infusion. In case of pharyngolaryngeal dysaesthesia oxaliplatin should be administered as 6-hour infusions.

Oxaliplatin diluted in 500 mL of 5% glucose solution must be infused either via a peripheral vein or central venous line over 2 hours. The infusion line must be adequately flushed with 5% dextrose solution (D5W) between oxaliplatin infusion and the administration of any other drug.

Oxaliplatin is incompatible in solution with alkaline medications or media and must not be mixed with these or administered simultaneously through the same infusion line. Do not simultaneously administer other drugs by the same infusion line.

Needles or intravenous administration sets containing aluminium parts that may come in contact with oxaliplatin should not be used. Aluminium has been reported to cause degradation of platinum compounds.

Oxaliplatin administration does not require hyperhydration. In the event of extravasation, administration must be discontinued immediately.

5.2.4.3 Possible adverse effects of oxaliplatin

Anaphylactic/anaphylactoid reactions

As is the case for other platinum compounds, hypersensitivity and anaphylactic/anaphylactoid reactions have been reported. These allergic reactions were similar in nature and severity to those reported with other platinum-containing compounds, i.e. rash, urticaria, erythema, pruritis, and, rarely, bronchospasm and hypotension. These reactions occur within minutes of administration (can also occur at other than the first cycle of treatment) and should be managed with appropriate supportive therapy (e.g. standard epinephrine, corticosteroid, and antihistamine therapy). Drug-related deaths associated with platinum compounds from this reaction have been reported.

Neurological

An acute, reversible primarily peripheral sensory neuropathy of early onset, occurring within hours or one to two days of dosing, resolves within 14 days, and frequently recurs with further dosing. The symptoms may be precipitated or exacerbated by exposure to cold temperature or cold objects and they usually present as transient paraesthesia, dysaesthesia and hypoesthesia in the hands, feet, perioral area, or throat. Jaw spasm, abnormal tongue sensation, dysarthria, eye pain, and a feeling of chest pressure have also been observed. The acute, reversible pattern of sensory neuropathy was observed in about 56% of study subjects who received oxaliplatin with infusional 5-FU/LV. In any individual cycle acute neurotoxicity was observed in approximately 30% of subjects. Ice (stomatitis prophylaxis) should be avoided during the infusion of oxaliplatin because cold temperature can exacerbate acute neurological symptoms.

An acute syndrome of pharyngolaryngeal dysaesthesia seen in 1-2% of subjects is characterized by subjective sensations of dysphagia or dyspnea, without any laryngospasm or bronchospasm (no stridor or wheezing).

A persistent (> 14 days), primarily peripheral, sensory neuropathy that is usually characterized by paraesthesias, dysaesthesias, hypoaesthesias, but may also include deficits in proprioception that can interfere with daily activities (e.g. writing, buttoning, swallowing, and proprioception-related ambulatory impairment). These forms of neuropathy occurred in 48% of the study subjects receiving oxaliplatin with infusional 5-FU/LV. Persistent neuropathy can occur without any prior acute neuropathy event. The majority of the subjects (80%) who developed grade 3 persistent neuropathy progressed from prior grade 1 or 2 events. These symptoms improve in most subjects upon discontinuation of oxaliplatin.

Pulmonary

Oxaliplatin has been associated with pulmonary fibrosis (0.7% of study subjects), which may be fatal. In case of unexplained respiratory symptoms such as non-productive cough, dyspnoea, crackles, or radiological pulmonary infiltrates, oxaliplatin should be discontinued until further pulmonary investigation excludes interstitial lung disease or pulmonary fibrosis.

Pregnancy and Lactation

To date there is no available information on safety of use in pregnant women. Based on pre-clinical findings, oxaliplatin is likely to be lethal and/or teratogenic to the human foetus at the recommended therapeutic dose, and is consequently not recommended during pregnancy, and subjects becoming pregnant during the study should discontinue oxaliplatin immediately. Excretion in breast milk has not been studied. Breast-feeding is contraindicated during oxaliplatin therapy.

Veno-occlusive Disease

Veno-occlusive disease, also known as sinusoidal obstruction syndrome, is a form of toxic liver injury characterized clinically by the development of hepatomegaly, ascites, and jaundice and histologically by diffuse damage in the centrilobular zone of the liver. Sequelae of this event include hepatomegaly, splenomegaly, portal hypertension, and oesophageal varices. The incidence of veno-occlusive disease associated with oxaliplatin usage is considered to be very rare. Standard clinical practice should be used for evaluation of veno-occlusive disease, including observation of liver and spleen size, history of or actual gastrointestinal bleeding, reversal of portal blood flow visualized by ultrasound, and possibly the development of oesophageal varices and bleeding or jaundice. Subjects who develop clinically significant veno-occlusive disease should discontinue oxaliplatin therapy.

Haematological

Oxaliplatin myelotoxicity is modest. The addition of oxaliplatin to 5-FU-based regimens is associated with increased incidence of low grades of thrombocytopenia, anaemia, and grade 3-4 neutropenia. Neutropenia is more frequent and severe with the use of bolus plus infusional bimonthly regimes of 5-FU/LV.

Gastrointestinal

Nausea, vomiting, constipation, diarrhoea, and stomatitis can occur. The incidence of severe diarrhoea seems to increase when oxaliplatin is added to the bolus daily times 5 regimen of 5-FU/LV. Subjects receiving 5-FU/LV containing regimens may experience bowel wall abnormalities (characterized by ileus and/or enterocolitis and thickening or ulceration of the small and/or large bowel) and infection (with or without neutropenia) requiring prolonged hospitalization.

Rash

Hand-foot skin reaction and injection site reactions have been seen.

Fever

Fever during infusion of oxaliplatin has been reported. Fever has been associated with the use of oxaliplatin.

Infection

May occur with normal ANC or unknown ANC.

Hepatic

Alkaline phosphatase, bilirubin, gamma-glutamyl transpeptidase (GGT), ALAT (SGPT), ASAT (SGOT) have all been reported to be elevated.

Renal

Subjects may experience some degree of elevation of serum creatinine. The incidence of grade 3/4 elevations is about 1% in previously treated subjects.

Cardiovascular

There has been reported incidence of thromboembolism.

Contraindications

Oxaliplatin is contraindicated in pregnant or breast-feeding women and in subjects

• with a known allergy against oxaliplatin or other platinum compounds

- with impaired bone marrow function
- with preexisting peripheral neuropathy
- with severe renal impairment.

For complete prescribing information, please refer to the SmPC (app. 6).

5.2.5 Modifications of therapy and dosage

5.2.5.1 General remarks

The handling of a combination of irradiation and hyperthermia with 5-FU and oxaliplatin is especially demanding with respect to toxicity and required dose adjustment, when compared to established dosing recommendations in case of adjuvant or palliative chemotherapy only:

- 1. There may be overlapping toxicities of the modalities,
- 2. Typical toxicities related to 5-FU infusion (hand-foot syndrome) and oxaliplatin (neuropathy) are expected to be rare and/or low intensity events during the therapy course of this protocol, as the cumulative doses in the combined modality course are rather low,
- 3. The main strategy of treatment adjustment, if required, should focus on the avoidance of treatment interruptions or premature termination.

The acute and protracted toxicity will be categorized and graded according to the NCI Common Terminology Criteria for Adverse Events, v 3.0 (CTC AE) (cf. appendix 3). In case of toxicities without severe or life-threatening sequelae (e.g. alopecia), the treatment should not be modified. If several toxicities of the same type occur simultaneously, the most pronounced of the proposed treatment adjustment procedure should be applied. When, according to the investigator's judgment, an adverse effect is exclusively related to one modality or drug (e.g. hand-foot syndrome due to protracted 5-FU infusion, neurotoxicity due to oxaliplatin), the dosage/intensity of the other drugs/modalities does not have to be modified.

In case of a dose necessary dose reduction, the reduced dosage will be administered during the whole remaining protocol treatment procedure. A subsequent re-escalation is not allowed. If, due to toxicity, the treatment has to be delayed for more than two weeks, the patient goes off protocol treatment and the end-of-treatment document page is reported. Each dose modification or treatment delay has to be documented in the CRF, including the respective reason.

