5.2.5.2 Specific modifications

It is decisive for dose modification, whether the toxicities occur

- 1. on the day of the oxaliplatin iv. application or
- 2. during the 5-FU infusion or
- 3. on another day of the treatment course

If a toxicity occurred during the interval between the chemotherapy courses, the drug dose in the subsequent course will be adapted according to the following table:

CTC grade	1	2	3	4
WBC	100%	100%	5-FU: 75%	5-FU: 75% L-OHP: 75%
Platelets	100%	100%	5-FU: 75%	5-FU: 75% L-OHP: 75%
Mucositis	100%	100%	5-FU: 75%	5-FU: 75% L-OHP: 75%
Diarrhea	100%	100%	5-FU: 75%	5-FU: 75% L-OHP: 75%
Skin	100%	100%	5-FU: 75%	Off treatment

If one of the following toxicity findings is still present on the day of the next chemotherapy administration:

- Diarrhea > grade 1
- Mucositis > grade 1
- Leukopenia > grade 2
- Thrombocytopenia > grade 1
- Other toxicities > grade 2

therapy has to be delayed for at least one week, and started when WBC have risen to > $3000/\mu$ I and platelets to > $100.000/\mu$ I and gastrointestinal toxicities have resolved. If necessary, a delay for a second week is allowed.

The following dose adjustments have to be undertaken in case of neurotoxicity caused by oxaliplatin:

Duration of toxicity			
	1-7 days	> 7 days	Persisiting durimng the chemotherapy interval
Cold related dysaesthesia	No change	No change	No change
Paraesthesia	No change	No change	Reduce by 25%
Paraesthesia with pain	No change	Reduce by 25%	stop L-OHP continue 5-FU
Paraesthesia with functional impairment	No change	Reduce by 50%	stop L-OHP continue 5-FU

In a small number of patients a special form of acute neuropathy, laryngopharyngeal dysaesthesia syndrome, may occur with a subjective feeling of dysphagia and dyspnoea but without objective signs of airway obstruction. This syndrome is not life-threatening and rapidly reversible without any treatment. During the following cycles the duration of infusion should be prolonged to 6 hours.

The specific neurotoxicity caused by oxaliplatin is recorded according to the following scale developed by Wassermann et al.:

Grade 1	Paraesthesia/Dysaesthesia < 7 days
Grade 2	Paraesthesia/Dysaesthesia 8-14 days
Grade 3	Paraesthesia/Dysaesthesia > 14 days
Grade 4	Paraesthesia/Dysaesthesia with functional impairment

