5.3.2 Modifications in case of toxicity

In case of acute diarrhea or hemorrhagic cystitis grade 4 during treatment, radiotherapy will be withheld until resolution of symptoms. When radiotherapy is withheld, chemotherapy and hyperthermia will not be delivered. RT will also be withheld for WBC <1.0 x 10^{9} /l, neutrophil count < 0.3 x 10^{9} /l and/or platelet count < 20 x 10^{9} /l. If the treatment delay exceeds two weeks, the patient goes off protocol treatment and the end-of-treatment document page is reported.

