5.7 EMERGENCY MANAGEMENT

In case of an emergency the coordinating investigator can be approached via the following phone/fax connection:

[name] (LKP) Univ. Hospital Erlangen Dept. of Radiation Oncology [name] [name] Germany [contact] [contact] Email: [contact]

Serious adverse events or reactions (cf. section 6.7.3 and 6.7.4), observed during the conduct of the study, have to be reported to the coordinating investigator/sponsor within 24 hours. A specific SAE form has to be filled.

5.8 **PREMATURE WITHDRAWAL OF AN INDIVIDUAL SUBJECT**

Patients will be removed from protocol treatment for the following reasons:

- disease progression,
- development of unacceptable toxicity
- treatment delay more than three weeks
- administration of any other anti-neoplastic medication or any other experimental drug
- consent withdrawn
- investigator decision in the best interest of the patient

- pregnancy or insufficient contraception
- loss to follow-up
- death

The time point of and reason for removal of a patient must be documented on the case report form. The investigator will attempt to complete all discharge procedures at the time a patient is discontinued from study treatment and to record further follow-up data, if required.

5.9 **PREMATURE STUDY TERMINATION BY THE SPONSOR/COORDINATING INVESTIGATOR**

At any time, the sponsor/coordinating investigator of the study may terminate the trial participation of an individual patient, as well as the whole trial, provisionally or permanently, if this is required by stringent medical, administrative or legal reasons (including insufficient patient recruitment), especially if severe and/or frequent adverse events occur, requiring a new risk/benefit evaluation.

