6.7 CRITERIA FOR SAFETY EVALUATION

6.7.1 Dose-limiting toxicity (DLT)

The following adverse reactions are defined as dose-limiting toxicity in the context of the **primary objective** of the trial to determine the feasibility rate (cf. section 7.2):

- Leukopenia or neutropenia of severity grade 3 or 4 with complications such as fever (> 38,5°C) or infection, or with a duration of > 7 days
- Thrombocytopenia of grade 3 or 4
- Non-hematological toxicity of grade 3 or 4 (except for nausea)
- Each toxicity leading to permanent discontinuation of at least one of the drugs or other treatment modalities, except for hyperthermia, if more than 60% of the scheduled applications occurred, or a delay of treatment of more than 3 weeks

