7.2 BIOSTATISTICAL ASPECTS

7.2.1 General design

The present trial is designed as a phase I/II study which aims at estimating the feasibility of the combined modality regimen consisting of chemoradiation including 5-FU/oxaliplatin and deep regional hyperthermia. The feasibility rate, i.e. the rate of patients without DLT (according to the definition in section XXX) *or* premature radiochemotherapy treatment withdrawal *or* hyperthermia delivery < 80%, is chosen as primary efficacy endpoint.

The estimation of the feasibility rate is to be based on an explorative pilot study, since immediate embarking on a large scale comparative efficacy trial would not be acceptable from the point of view of resources. Moreover, this would induce ethical objections, as it does not seem to be justifiable to expose a large number of patients to an experimental approach without any exploratory indications of an improved risk-benefit ratio.

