7.2.3 Evaluation categories of patients

Patients not fulfilling the selection criteria of the trial ("non-eligible") will be excluded from the statistical analysis. Only casuistic reports will be provided for this group. All other patients will primarily be evaluated in an intent-to-treat analysis.

If a patient goes off treatment during the first two cycles for clearly other reasons than toxicity, he will not be included in the feasibility rate finding process and has to be replaced.

All patients having received at least one application of therapy are generally evaluable for toxicity.

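### The removal list in 5.8 sets a three-week delay limit without excluding toxicity delays, for which 5.2.5.1 and 5.3.2 set two weeks

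*Protocol*

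**What the plan says.** Four places in the Protocol deal with how long treatment may be held.

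- **5.2.5.1 General remarks:** if treatment, because of toxicity, "has to be delayed for more than two weeks, the patient goes off protocol treatment".
- **5.2.5.2 Specific modifications:** when certain toxicities persist on the day chemotherapy is next due, it is put off for at least one week. "If necessary, a delay for a second week is allowed". No third week is offered.
- **5.3.2 (radiotherapy, modifications for toxicity):** "If the treatment delay exceeds two weeks, the patient goes off protocol treatment".
- **5.8 Premature withdrawal of an individual subject:** the reasons for removal from protocol treatment include "treatment delay more than three weeks", with no cause stated. A separate bullet covers unacceptable toxicity.

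Three further places decide how such a patient is scored.

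- **6.7.1 (DLT):** counts "Each toxicity leading to permanent discontinuation of at least one of the drugs or other treatment modalities" (with an exception for hyperthermia), "or a delay of treatment of more than 3 weeks".
- **7.2.1:** also counts "premature radiochemotherapy treatment withdrawal" as non-feasible.
- **7.2.3:** of a patient who stops therapy in cycle 1 or 2, it says: "for clearly other reasons than toxicity, he will not be included in the feasibility rate finding process and has to be replaced". A patient removed for toxicity therefore stays in the denominator as a failure.

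**The concern.** The rules for holding and restarting treatment put the limit for a toxicity delay at two weeks. The list a site consults when deciding on removal puts it at three and does not set toxicity aside. No sentence says which governs.

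A three-week figure also appears in 6.7.1, where it does concern toxicity, so the 5.8 figure does not read as an obvious slip. In addition, 5.2.5.1 tells sites that avoiding interruption and early termination is the main aim when adjusting treatment, which could push a site towards the longer limit.

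The primary endpoint is at stake. Two sites in a multi-institutional trial could score the same clinical course in opposite ways, and the feasibility rate would then partly reflect which section each site read.

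**Working it through.** **1. The plan's own design.** Inputs from 7.2.2: unacceptable feasibility rate 0.70, promising rate 0.85, type I error 0.05, power 0.80, Simon optimal two-stage design. Let X be the feasible patients among the first 19 and Y those among the next 40. Stage 1 stops at five or more failures, i.e. X ≤ 14. With final cut-off r,

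P(accept | p) = Σ over x = 15 to 19 of P(X = x | 19, p) × P(Y > r − x | 40, p).

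An exact binomial search returns 14/19 and 46/59, with type I error 0.0494, power 0.807 and expected sample size 30.3 at p = 0.70. The stated 19 and 59 are reproduced. The cut-off of 46 comes from the search; the protocol does not print it.

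**2. The limits side by side.**

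| Section | Function | Limit | Cause |
|---|---|---|---|
| 5.2.5.1 | off protocol treatment | > 2 weeks | toxicity |
| 5.2.5.2 | cap on a chemotherapy hold | 1 + 1 weeks | toxicity |
| 5.3.2 | off protocol treatment | > 2 weeks | toxicity |
| 5.8 | off protocol treatment | > 3 weeks | not stated |
| 6.7.1 | DLT criterion | > 3 weeks | toxicity |

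The first four rows govern conduct, and 5.8 is the odd one out. Section 5.2.5.2 contains no removal wording; it only caps the hold. The last row governs scoring, not removal.

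**3. One patient, two scores.** Take a toxicity delay of 15 to 21 days with no other event.

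- Under 5.2.5.1 or 5.3.2 the patient is removed. This is a permanent discontinuation for toxicity (6.7.1) and a premature withdrawal (7.2.1). It counts as a failure and the patient is not replaced (7.2.3).
- Under 5.8 alone the patient resumes. The delay does not exceed three weeks, so the 6.7.1 delay clause is not met. The patient can count as feasible.

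**4. Who can be in this position.**

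- Radiotherapy holds for diarrhoea or haemorrhagic cystitis under 5.3.2 require grade 4, which is already a DLT.
- Leukopenia holds under 5.2.5.2 start above grade 2. Grade 3 or 4 with fever, infection or duration over 7 days is already a DLT, so little remains.
- Diarrhoea, mucositis and thrombocytopenia hold chemotherapy from grade 2, which is not a DLT. This is the main group.
- Section 5.4.2 lets radiotherapy continue during a chemotherapy hold. A day 9 dose put off by 15 to 21 days falls on day 24 to 30 (9 + 15, 9 + 21), inside the five weeks of radiotherapy. A course due on day 22 falls on day 37 to 43, after the 45 Gy phase.

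**5. Size.** One patient scored differently moves the final rate by 1/59 = 0.017. The protocol gives no frequency for such delays, so the table assumes a share of patients who have a 15 to 21 day toxicity delay and no other failure. It compares all sites on one reading with all sites on the other.

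| Assumed share | Power, if the rate is 85% on the three-week reading and these patients are failed | Acceptance, if the rate is 70% on the two-week reading and these patients are passed |
|---|---|---|
| 0% | 0.807 | 0.049 |
| 1% | 0.754 | 0.068 |
| 2% | 0.695 | 0.091 |
| 3% | 0.631 | 0.120 |
| 5% | 0.495 | 0.197 |

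Of 59 patients, 1% is 0.6 and 5% is 3.0. The table shows how sensitive the design is to scoring, not how often the problem will arise.

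**The case against.** The best defence is that both limits can be obeyed together. Sections 5.2.5.1 and 5.3.2 are specific to toxicity. The 5.8 bullet is general and lists grounds for removal; it gives no permission to continue up to three weeks. Removal at two weeks can be recorded under the separate unacceptable-toxicity bullet. To resume after 15 to 21 days a site must set aside the very sections that govern holds. This stands in so far as a careful site has a compliant course, the stricter rule. It does not remove the conflict, because 5.8 neither limits itself to other causes nor refers to the two-week rule.

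It is also fair to say that the day 9 example is not clean. A 14-day delay already reaches day 23, itself an oxaliplatin day, and the protocol does not say whether a dose given later is delayed or omitted. That narrows the group further.

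A reader might infer that the three-week delay clause in 6.7.1 can never be met and should be cut to two weeks. The document does not support this. For a single hold under the two-week rule the clause is redundant, since a removed patient is already a DLT by discontinuation. But 5.2.5.2 sets its cap at each due administration, and 6.7.1 does not say whether delay means one hold or the total. If it is the total, holds of 14 and 8 days add to 22 days, more than three weeks, with neither exceeding two. The clause may then catch patients whom the discontinuation wording misses. Cutting it to two weeks could turn permitted combined holds into DLTs and lower measured feasibility.

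**Conclusion.** The inconsistency is real and lies in one bullet. Section 5.8 gives three weeks without excluding toxicity, against two weeks in 5.2.5.1 and 5.3.2 and the matching cap in 5.2.5.2. It reaches the primary endpoint through 6.7.1, 7.2.1 and 7.2.3 and should be fixed, but it does not undermine the design: 19 and 59 stand.

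The size is unknown. What can be said firmly is 1.7 points on the final rate per patient scored differently. The power and acceptance figures rest on an assumed share of affected patients and on all sites taking the same reading.

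A reader might also infer a sizeable risk to the stage 1 decision. If one of the first 19 patients is in the window, that score decides the outcome when exactly 4 of the other 18 fail, which has probability 15.9% to 21.5% for failure rates of 15% to 30%. That figure is conditional on such a patient existing, and the protocol does not say how often that happens, so it is not an estimate of the risk to the trial. Nor does the final conclusion rest on the rate alone: 7.2.2 also weighs its confidence interval, treatment delivery and the full toxicity profile.

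**What to change.** Change the 5.8 bullet in one of two ways:

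- reword it as *delay due to toxicity of more than two weeks (see 5.2.5.1, 5.3.2)*; or
- keep three weeks and state that it applies only to delays from causes other than toxicity.

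Leave 5.2.5.1, 5.2.5.2, 5.3.2 and the 6.7.1 delay clause as they are.

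The cost is one line of wording and notice to the sites. It probably needs a formal amendment under 11.7, with a new application to the competent authority and the ethics committee, because a removal limit may affect patient safety and study procedures. Sample size and stopping rule are unaffected.
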